A.1. Specific Aims Substantial evidence affirms that the “Holy Grail” of health care delivery science, getting the right care to the right patient at the right time, is not achieved consistently in the care of teens with type 1 diabetes (T1D). Technological advances such as continuous subcutaneous insulin infusion (CSII; insulin pump) and continuous glucose monitoring (CGM) offer great potential for improved glycemic control and greater lifestyle flexibility, but adolescents, compared with adults, derive less benefit from incorporating these advances into their care.¹⁻²⁰ While any diabetes clinician can readily point to instances in which CSII or CGM have markedly improved T1D outcomes in some adolescents, the research shows that adolescents in aggregate do not realize improved outcomes with these technologies. This suggests that adolescent candidates for CSII and CGM either are not selected carefully enough, are passive participants in decision making about their health care, are inadequately prepared for the practical demands of using these technologies optimally, or have not anticipated or circumvented their key personal barriers to effective incorporation of these technologies into care. The planned work will complement [name] ongoing NIH-funded trial (R01-DK080831) of a behavioral intervention to enhance teens’ benefit from CGM use by testing an intervention designed to facilitate the initial incorporation of CSII and CGM into adolescents’ T1D care. We will determine if a Shared Medical Decision Making (SMDM) intervention can improve the quality of decision making and behavioral and metabolic outcomes among adolescents with type 1 diabetes (T1D) who are candidates for either CSII or CGM. Leading health care organizations advocate shared decision making as a central aspect of a learning health system and in support of efforts to provide reliable evidence for making informed healthcare decisions that more effectively engage patients as partners in their own care.²¹⁻²² Specifically, the Patient Centered Outcomes Research Institute intends to provide patients with enhanced understanding of available prevention and treatment options, as well as the science that supports these options.²² We propose a 3-year program of research with these Specific Aims:

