Each parent/adolescent dyad will receive a \$25 gift card to a discount retail chain after completing the measurement protocol at Visits 1, 3 and 5, which are the most burdensome of the visits. At each study visit in which an adolescent brings either an insulin pump or CGM to the visit for downloading, the adolescent will receive a \$5 gift card for each such device that is downloaded.

Measures obtained at Baseline only

Demographic characteristics will be measured at study entry using a General Information Form as in our previous studies. This measure ascertains the child's age, diabetes duration, gender, race/ethnicity, and relevant medical history (including past CSII or CGM use) and the parents' income, educational level, occupational category, family structure, race/ethnicity, gender and age. The Hollingshead Four Factor Index of Social Status¹⁵⁹ will be calculated to quantify household socioeconomic status. Participants will be asked to indicate their preferred mode of contact from study staff (e.g. text, phone, e-mail, specific social media). Administration time is about 15 minutes.

Rapid Estimate of Adult/Adolescent Literacy in Medicine This brief test of health literacy will be administered in person to parents and adolescents by the research coordinator at baseline.¹⁶⁰

Diabetes Numeracy Test This 14-item test of numeracy skills pertinent to T1D care will be administered in person to parents and adolescents by the research coordinator at baseline.¹⁶¹

Measures obtained at all 5 quarterly clinic visits

Glycated hemoglobin: Finger-Stick blood samples will be obtained at each quarterly visit and glycated hemoglobin (HbA_{1C}) will be determined using the point of care device currently used at each clinic (typically a DCA2000 or DCA2000plus). These devices have been found to yield results that are highly correlated with benchmark central laboratory assays and that are considered to be acceptable outcomes measures in diabetes clinical trials. HbA_{1C} reflects average glycemia over the prior 2-3 months and is considered a secondary outcome measure in this study.

Hypoglycemia Diary: Parents will record each episode of moderately severe (symptomatic and requiring

assistance from others) or severe hypoglycemia (with seizure or loss of consciousness) using a diary form developed for this purpose in [name] ongoing CGM trial. Frequency of moderately severe and severe hypoglycemia is considered a secondary outcome measure in this study.

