Insulin Pump and Continuous Glucose Monitor Downloads: Device downloads will be the primary outcome measures since these measures will reflect the extent to which participants demonstrate optimal use of CSII or CGM. At Visits 2 through 5, staff will download insulin pumps and CGM devices for those using them, or adolescents can e-mail data download files to the research team prior to each of those visits. For insulin pump users, the number of bolus infusions, number of times the "bolus wizard" was used and percentage of days on which fewer than 3 bolus infusions of insulin were registered will be recorded. For CGM users, the mean number of hours per day of stored CGM data will be captured from device downloads. Complete cessation of the chosen treatment will also be recorded if it occurs, which is expected to be much more common among adopters of CGM compared with adopters of CSII. Each of these scores will be transformed into z-scores relative to the full sample, permitting combined treatment of these measures in the planned analyses. Another analytic option would be to utilize an operational criterion to dichotomize patients into "Optimal" or "Suboptimal" users of CSII or CGM for the purpose of testing logistic regression models of SMDM effects. This determination will be made by [name], the project statistician.

Measures obtained at the first post-decision visit only

These measures will be obtained at the next study visit for those participants who have reached a decision. The Measurement schedule depicts this as Visit 2, which is expected to be the case for most participants, but some participants may take longer to reach a decision.

SMDM Satisfaction Scale: This measure, constructed for this study, will be completed only by adolescents and parents at the next study visit following their actual receipt and initialization of the chosen device (CGM or insulin pump). This scale is to be completed only by SMDM participants.

SMDM Satisfaction Scale- Clinician Form: This measure will be completed by clinicians at the first visit after each parent and adolescent in the SMDM group have reached a decision about the technology of interest (pump or CGM) to assess their level of satisfaction with how helpful the decision aid was for the patient/parent in the decision making process. The measure includes 5 items rated on a 5 point scale and space for the clinician to write additional comments. This will be completed for patients in the SMDM group only.

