Data Management and Statistical Analysis Plans The primary efficacy endpoints are indices of extent of engagement in CSII (mean number of bolus infusions/day; mean number of uses of "wizard" functions/day) or CGM use (mean number of hours of CGM use/day); and measures of decision quality (Test of CSII or CGM Knowledge; SURE Test; Decision Regret Scale; Diabetes Technology Questionnaire) at each post-decision visit. Secondary efficacy endpoints will include: HbA_{1c} measured quarterly, treatment adherence (DSMP-SR parent and youth) total scores obtained at Visits 1, 3 and 5; and Hypoglycemia Diary obtained at each quarterly clinic visit.

The Full Analysis Set will consist of all participants who provided at least one post baseline assessment record. The Completer Analysis set will include all participants who provided all post baseline primary efficacy assessment results.¹⁶⁶⁻¹¹⁶⁸ Efficacy analyses will be performed on both sets, providing both "Intention to Treat" (Full Analysis Set) and "Per-Protocol" (Completer Analysis Set) analyses. All collected data will be summarized in graphs and tables. Categorical variables will be summarized using frequencies and percentages, while quantitative variables will be described by presenting mean, median, standard deviation (or standard error of mean), minimum and maximum. Data will be summarized by group (SMDM and UCP) and type of medical decision (CSII or CGM) as well as assessment time points. Besides tabular presentation, graphical presentations of some important variables related to primary and secondary endpoints will be provided.

Assumptions for all proposed models will be checked before statistical analyses.¹⁶⁶⁻¹⁶⁸ Appropriate transformations or non-parametric methods will be used in cases of violated model assumptions. For graphical comparison of data that are sufficiently normally distributed, group means and SE of mean will be presented via bar charts. In case of substantial deviation from normality, side by side boxplots will be used for graphical comparisons. Exploratory Subgroup analyses will be conducted as needed. All tests will be performed against a two-sided alternative at the $\alpha = 0.05$ significance level and a 95% confidence interval and/or a p-value will be provided for inferential purposes. Data from all clinics will be pooled for the analyses. All analyses will be performed using the most recent version of the SAS statistical software package.

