Demographic and baseline characteristics (age, race, ethnicity, family composition, marital status, SES), primary and secondary end points, and biochemical, psychological, and behavioral variables will be summarized by intervention groups. One way analysis of variance (ANOVA) of each continuous baseline characteristic and a Fisher exact test/chi-square test/CMH test for each categorical variable will be used to compare the intervention groups at baseline. These comparisons will be used to evaluate the balance of demographic and baseline characteristics among intervention groups. Analyses of primary and secondary end points will be adjusted for significantly imbalanced baseline characteristics. For those measures completed separately by parents and youths, when parent and youth scores are correlated at $r > .70$, a combined parent-adolescent score for that variable will enter analyses. Otherwise, separate analyses will be completed on parent and adolescent scores. A mixed models (or multilevel modeling) approach will be used to test the hypotheses listed below.¹⁶⁹⁻¹⁷² The methods advocated by Holmbeck¹⁷³ will be used to evaluate baseline variables that moderate/predict SMDM-UCP treatment effects on primary study outcomes. Candidate moderator variables will include SES, youth age and gender, race/ethnicity, family structure, and health literacy and numeracy. The methods advocated by Holmbeck¹⁷³ will also be used to evaluate variables that may mediate SMDM-UCP treatment effects on primary study outcomes. In each case, these will include measures that are obtained serially and concurrently with the primary study endpoints. SAS subroutines for addressing the potential confounding influences of time- dependent covariates (e.g. youth age) will be employed as needed in these mediational analyses. With five measurement points for HbA_{1c} and hypoglycemia, the proposed mixed models approach will be capable of detecting longitudinal associations among study variables that are non-linear in form.

Hypothesis 1: Compared to UCP, the SMDM group will have significantly more favorable status in terms of indices of optimal use of CSII or CGM, scores on the CSII or CGM Knowledge Test, SURE Test, Decision Regret Scale, Diabetes Technology Questionnaire and SMDM Satisfaction Scale at each follow-up measurement point.

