Hypothesis 2: Compared to UCP, the SMDM group will have significantly more favorable status in terms of scores for treatment adherence (DSMP-SR), HbA_{1c}, and frequency of moderately severe or severe hypoglycemia at each follow-up measurement point.

Hypothesis 3: Effects of SMDM on indices of optimal use of, and satisfaction with, CSII or CGM will be mediated by changes in the measures of decision quality (Test of CSII or CGM Knowledge, Decision RegretScale, SURE Test, Decision Satisfaction Scale).

Hypothesis 4: Significant moderators of benefit from SMDM along the measured outcomes will include baseline measures of socioeconomic status, health literacy and numeracy, youth age, and family structure.

Hypothesis 5: SMDM will have indistinguishable beneficial effects on the primary study outcomes regardless of which clinical decision (CSII or CGM) was the focus of the SMDM intervention.

Statistical Power Statistical power to detect treatment effects of interest on the primary endpoints was assessed using the online DSS Research Statistical Power Calculator.¹⁷⁴ With enrollment of 166 eligible youth and parents and attrition of 10% over the 12-month study, and a resulting “Completer” sample size of 150, the study will have statistical power of .87 to detect a moderate treatment effect of ~0.4 SD on the measures of decision quality and CSII or CGM optimal use. Even though statistical power remains adequate for detection of somewhat smaller treatment effects, effects of less magnitude are unlikely to have sufficient clinical significance to warrant the added cost and inconvenience of implementing SMDM.

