Five parents and their seven adolescents with T1D were recruited to serve as members of a Family Advisory Council. They were selected to reflect diverse representation in terms of Nemours sites, socioeconomic status, race/ethnicity, gender and prior experience related to insulin pump therapy and continuous glucose monitoring. Each FAC dyad will be paid \$500 annually to compensate them for expenses they incur due to their FAC participation. In constituting this group, we began by carefully examining the participants in [name] ongoing NIH-funded trial of continuous glucose monitoring, from which we were able to identify adolescents who did or did not experience CGM use and who did or did not demonstrate glycemic or quality of life benefits from doing so. This group of 104 research participants consists of 67% non-Hispanic Caucasians, 21% African-Americans and 12% Hispanics, with very diverse educational attainment and household income. Similarly, we will be able to identify adolescents whose insulin delivery modalities were either insulin pumps or multiple daily insulin injections during that study.

The FAC will be convened in monthly meetings using video or telephone conferencing facilities that are in place at all Nemours operating entities. Each meeting will be audio-recorded and minutes will be taken and distributed to all members. The FAC will select its own chair, who will prepare the meeting agendas and manage the discussion of the specific agenda items. The FAC will be considered advisory to the research team, in that their recommendations will be given very serious consideration, but final decisions regarding study design, implementation or interpretation will rest with [name] and the Co-Investigators. The initial charge of the FAC will consist of review of, and commentary on, the study protocol, procedure manual, and human subjects protection plan. Since an external and independent Data and Safety Monitoring Board is

unnecessary for this research since it poses minimal risk to participants, the FAC (with participation by [name], [name] and one of the endocrinologists) will provide study oversight regarding the recruitment experience, and the occurrence of any data quality issues, threats to privacy or confidentiality, other unanticipated problems, participant complaints or other such issues.

Prospective FAC members have received this list of expectations regarding their involvement :

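### Device-use models take baseline covariates only after a significant balance test; past device use and Visit 1 youth adherence, both already collected, should be fixed in advance

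*Combined protocol and SAP*

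**What the plan says.** A.1 presents the trial as "testing an intervention designed to facilitate the initial incorporation of CSII and CGM into" the care of adolescents with type 1 diabetes. B.3 names pump and CGM downloads as the primary outcome measures and sets their timing: "At Visits 2 through 5, staff will download insulin pumps and CGM devices for those using them". The schedule in B.4 likewise has no Visit 1 entry for the device-use profiles.

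Two relevant baseline items are collected. The General Information Form takes "relevant medical history (including past CSII or CGM use"). The DSMP-SR is completed by youth and parent at Visits 1, 3 and 5. Under B.1, randomisation follows completion of all baseline measures, so both items should be available for every randomised youth.

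B.5 calls for mixed models but lists no fixed covariates for Hypothesis 1. It compares the arms at baseline with ANOVA or categorical tests and then states: "Analyses of primary and secondary end points will be adjusted for significantly imbalanced baseline characteristics". The variables summarised by arm include the secondary endpoints and behavioural variables, which takes in DSMP-SR. Past device use is not named there. Neither variable is among the candidate moderators in B.5 or in Hypothesis 4.

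The eligibility lists in B.1 and C.3 do not exclude youths who used the device before.

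**The concern.** A baseline covariate earns its place by predicting the outcome, not by differing between arms. Under randomisation any difference is chance, so a significance test selects covariates by the accident of allocation and usually selects none.

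This matters for device use because there is no pre-treatment value to adjust for, and the available substitutes are left to the test. The plan gives some reason to think past use is prognostic: B.2 says, from earlier trials, that few adolescents who do not benefit at first go on to benefit later. A youth who tried a device and stopped may differ from a first-time candidate, and a youth with good adherence at entry may use a device more consistently.

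Two things are at stake: precision that the data already collected could supply, and the handling of imbalances too small to trigger the rule but large enough to move the estimate.

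**Working it through.** **Inputs.** Test: "two-sided alternative at the $\alpha = 0.05$ significance level" (B.5). Sample: "With enrollment of 166 eligible youth and parents and attrition of 10% over the 12-month study" (B.5, Statistical Power); 166 × 0.9 = 149.4, which the plan takes as 150, or 75 per arm at equal allocation. Target effect: 0.4 SD. The correlation R between the covariates and device use is not in the documents; 0.2 to 0.5 is an assumption. The nearest documented figures concern another outcome: DSMP-SR with HbA1c, .37 for youths and .46 for parents (B.3).

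**Step 1: the plan's own figure.** B.5 states "the study will have statistical power of .87 to detect a moderate treatment effect of ~0.4 SD". For one two-arm contrast, power = Φ(0.4 × √(75/2) − 1.96) = Φ(2.449 − 1.960) = 0.688 (0.682 with the noncentral t). The stated .87 is not reproduced; at 75 per arm it needs about 0.50 SD. It would also fit covariates with R of about 0.61, or the mean of four visits with a within-person correlation of about 0.51, but the plan states neither. That is a separate matter; 0.688 is the reference below.

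**Step 2: prespecified adjustment.** The residual SD becomes √(1 − R²), so power = Φ(0.4 × √(n/2) / √(1 − R²) − 1.96). The same precision without adjustment would need 1/(1 − R²) times the patients.

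| R | Power, 75 per arm | Equivalent extra patients | Power, 50 per arm |
|---|---|---|---|
| 0 | 0.688 | 0% | 0.516 |
| 0.2 | 0.705 | 4% | 0.532 |
| 0.3 | 0.728 | 10% | 0.554 |
| 0.4 | 0.762 | 19% | 0.588 |
| 0.5 | 0.807 | 33% | 0.637 |

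The 50-per-arm column is illustrative: downloads exist only for youths who take up a device, and the documents do not project that number.

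**Step 3: what the B.5 rule recovers.** Simulation with 20,000 runs per setting, 75 per arm, one normal covariate, effect 0.4 SD:

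| R | Never adjust | Adjust only if p < 0.05 at baseline | Always adjust |
|---|---|---|---|
| 0.3 | 0.684 | 0.687 | 0.722 |
| 0.4 | 0.686 | 0.692 | 0.758 |
| 0.5 | 0.686 | 0.696 | 0.798 |

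The rule triggered in 4.7% to 5.2% of runs. At R = 0.5 it recovered (0.696 − 0.686)/(0.798 − 0.686) = 9% of the gain; at R = 0.3, 0.003/0.038 = 8%.

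**Step 4: imbalance that escapes the rule.** The largest non-significant difference in a standardised covariate is 1.96 × √(2/75) = 0.32 SD. The shift in the unadjusted effect is R × 0.32: 0.064 SD at R = 0.2, 0.096 at 0.3 and 0.160 at 0.5, or 16% to 40% of the 0.4 SD target. This is the worst case. A one-standard-error imbalance is √(2/75) = 0.163 SD, and shifts the effect by 0.03 to 0.08 SD over the same range of R.

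**Step 5: type I error.** With no true effect, the rule rejected in 4.3% to 5.0% of runs overall. In runs with a near-significant imbalance (|t| between 1.28 and the cut-off), it rejected in 6.3% to 8.5%; always adjusting gave 4.7% to 5.1% in those runs.

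**The case against.** The strongest reply is that B.5 does contain an adjustment rule. DSMP-SR falls under it as a secondary endpoint, and past use could do so as a categorical baseline item. A reader might infer that neither variable can ever enter a Hypothesis 1 model. The documents do not support that: either may enter if it tests as imbalanced. The accurate criticism is that entry depends on the test.

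A reader might also infer that the trial result is biased. It is not, on average. A sub-threshold imbalance is conditional error in the trial at hand, and Step 5 shows that overall type I error is kept.

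Nor is device use alone. The SURE Test and Decision Regret Scale, also primary in B.5, start at Visit 3, and the plan fixes covariates for no endpoint. A missing pre-device value is inherent for new adopters and is not itself a fault.

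It is tempting to say that former users contradict the aim of initial incorporation, or that they will come from the sites' earlier CGM trial. The A.1 phrase describes purpose; B.1 defines the population as youths with a current pump or CGM decision, and a former user reconsidering a device qualifies. The Part D sentence on being able to "identify adolescents who did or did not experience CGM use" is about choosing Family Advisory Council members. That trial is described as ongoing, and B.1 bars concurrent participation in other research with adherence or glycemic outcomes. The documents give no count of former users.

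Finally, covariates do not repair the power figure in Step 1 or the fact that device use is observed only in those who select a device. All of this stands. None of it shows that a balance test is a sound way to choose covariates.

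**Conclusion.** The concern holds as a point about prespecification. B.5 leaves two plausible, already collected predictors of device use to a test that is significant about one time in twenty per covariate, and so forgoes nearly all the precision they could give.

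The size rests on an assumed R. At 0.2 the power gain is about 2 points; at 0.5 it is about 12 points (0.688 to 0.807). The largest imbalance that escapes the rule would shift the estimate by 0.06 to 0.16 SD. The figures are for a single contrast with 75 per arm; the gain in the repeated-measures model will also depend on the within-person correlation, which the plan does not give.

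The change is worth making because it costs almost nothing, not because the present rule invalidates the test.

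**What to change.** In B.5, replace the significance-test rule for the device-use models with two covariates that enter regardless of any balance test:

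- past use, yes or no from the General Information Form, of the device under consideration at randomisation; for youths who are candidates for both devices, past use of the device whose use is being modelled;
- the Visit 1 youth DSMP-SR total score.

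The cost is two degrees of freedom and a change of SAP wording. Nothing new is collected.

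An analysis that leaves out past users of the device is optional. If done, label it exploratory, because first-time use is not an eligibility requirement and the exclusion would shrink an endpoint already limited to device users.
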